7 TRIAL PROCEDURES

	Research team activities
Information about the trial	The approved study posters will be available in A&E and at swabbing stations, to inform patients about the availability of the trial for those who test positive. Participant can express interest in participating when swabbed and details for contact can be taken by the research team, or patients can email the research team later to express interest. Participants may hear about the trial through other external sources eg the approved posters or the media and may contact the research team.
At swabbing station	Patients will be approached by a member of the research team at the swabbing station and asked if they have symptoms. If they do, they will be asked if they have time to talk and the research team member will explain about the study and ask if the patient is interested in taking away any further information about the study. If they say yes, they will be given the Patient Information Sheet. The research team member will ask if they are happy to provide their contact details so that they can be contacted after they receive their test result.
Patients contacting the Research Team Directly	Patients who have heard about the trial through the media or by seeing one of the approved posters may contact the Research Team directly. If they are able to show the positive swab test result that they have had a within the last 5 days, the research team will email them the Patient Information Sheet. The research team will then contact them as below
Telephone Contact	Patients who have given their contact details at a swabbing station or A&E will be telephoned after 24hours to see if they have tested positive for COVID-19, and if they have they are asked if they are interested in taking part in the study. The member of the research team will then check whether they have read the Patient Information Sheet and answer any questions.
Patient Information Sheet (PIS)	PIS will be emailed to patients who test positive and express interest in the study, for them to read and consider taking part.
Follow up telephone call within 5 days of a positive swab; Verbal Consent and Baseline data collection	Opportunity to raise and discuss any questions about the trial or PIS ^(a) . Eligibility criteria will be checked and electronic or verbal consent will be received. An eligible patient can decline to participate without having to give any reason. After consent, the research team will collect baseline demographics, VAS score, patient symptoms. ^(a)
Ineligible patients	If anyone does not meet the eligibility criteria the research team will explain why and ensure that they have time to ask any questions.
Randomisation and collection of trial treatment	Patients will be randomised to active or placebo liquid and a 14 day supply of study liquid dispensed to take home and start straight away. This can either be collected by a family member or friend and dropped to the patient's doorstep – or the research team will drop to the doorstep so that everyone has a chance to take part. If a participant lives further away the liquid will be delivered to their home address by courier.
Follow Up visits on day 3, 7, 10, 14 and 28	All follow up visits will occur either by phone, text or email depending on participant preference at day to collect the following data: 
 • Current symptoms

BERRY Protocol v 6.2 22.07.2021 IRAS 282732

	
 • How well are you feeling VAS score 0 -100 (0 will be recorded in the case of death) • What are your current symptoms? • Have you started any new medications? • Have you missed any doses of your study liquid? • Experienced any adverse events? • At day 14 – if a participant verbally consented initially, they will be asked to sign a paper consent form which was sent out with their trial liquid and return it in the research team for filing. At day 14 they will also be reminded that they need to stop taking their study liquid.
Notes	(a) This limits the exposure of the research team to the virus during later collection of written consent

BERRY Protocol v 6.2 22.07.2021 IRAS 282732

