8.6 Dosage schedules

All participants will take a fixed dosage of 15ml orally four times a day. Total daily dose 60ml. Missed doses can be taken at any time. If the patient vomits shortly after taking a dose they can repeat the dose.

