8.11 Assessment of compliance with treatment

Participants will be asked to confirm their compliance during planned telephone interviews with research staff on days 3,7,10 and 14.

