9.7 Overdose

Participants will be advised in the PIS to contact the research team on for advice if they believe they have taken too much Sambucol/Placebo or an overdose. Participants will also be asked about their compliance with the recommended dosage during telephone consultations with the Research Staff. Emergency contact for 24hr

Overdose definition: More than 50 % excess dosage (> 90ml) in any 24 hour period. Identified during participant consultations. In the event of a confirmed overdose the participant will be withdrawn from the trial.

Any overdose event will be recorded as a protocol deviation and reported to the Sponsor.

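### Section 8.6 allows catch-up and repeat doses with no 24-hour maximum, so a participant who follows it can meet the overdose and withdrawal rule in section 9.7

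*Combined protocol and SAP*

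**What the plan says.** Section 8.6 fixes the dose at 15 ml four times daily, 60 ml in total. It then says "Missed doses can be taken at any time" and "If the patient vomits shortly after taking a dose they can repeat the dose". It sets no maximum for either kind of extra dose. The label text in Appendix 1 repeats the four-times-daily instruction and also gives no maximum.

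Section 9.7 sets the limit: "Overdose definition: More than 50 % excess dosage (> 90ml) in any 24 hour period. Identified during participant consultations". The consequence is mandatory: "In the event of a confirmed overdose the participant will be withdrawn from the trial". Sections 8.6 and 9.7 do not refer to each other.

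On recording intake, the follow-up list in section 7 asks "Have you missed any doses of your study liquid". Section 7.7 has a compliance row at every follow-up contact and at early exit, without saying what is recorded. Section 9.7 adds: "Participants will also be asked about their compliance with the recommended dosage during telephone consultations with the Research Staff". Section 8.4.5 limits accountability to the pharmacy stock log and the batch number issued.

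On analysis, section 10.3.2 makes ANCOVA of the day-10 score by ITT the primary analysis. It names a per-protocol analysis as a possible sensitivity analysis and does not define that set. Section 7.10 stops data collection once consent is withdrawn, and section 10.8 omits missing values without imputation.

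**The concern.** Read together, the dosing instruction and the overdose rule can put a compliant participant in breach. Someone who misses most of a day while ill and then catches up, or who vomits several doses and repeats them, is doing what 8.6 permits. Section 9.7 may still require that person's withdrawal. Extra doses are foreseeable, since section 9.2 lists nausea and vomiting among the known manifestations of COVID-19.

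Detection is also uneven. A participant acting within 8.6 has little reason to think that too much was taken, and so little reason to call the team. Nothing listed asks for the amount taken in a 24-hour period. Whether a breach comes to light may depend on how a conversation happens to go.

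What is at stake is the outcome data of anyone withdrawn this way. If the withdrawal also ends data collection and happens before day 10, the primary outcome is missing and the analysis omits that participant.

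A smaller issue sits beside this. A question about whether any doses were missed does not, as worded, yield the number missed. Without a number, a per-protocol set based on the share of doses taken could not be formed later.

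**Working it through.** **Inputs.** Dose 15 ml, four times a day, 60 ml daily (8.6). Overdose above 90 ml in 24 hours (9.7). Supply for 14 days in 120 ml bottles (sections 7 and 8.1). Planned size 172 analysed and 204 recruited (10.1). Contacts at days 3, 7, 10 and 14 during treatment (8.11).

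**The plan's own limit.** A 50% excess over 60 ml is 1.5 × 60 = 90 ml, as stated. That is 90 / 15 = 6 doses.

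**Volume in 24 hours with k extra doses on top of the four scheduled:** 60 + 15k ml.

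| Extra doses k | Volume | Above 90 ml? |
|---|---|---|
| 1 | 75 ml | no |
| 2 | 90 ml | no, at the limit |
| 3 | 105 ml | yes |
| 4 (a whole missed day) | 120 ml | yes |

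The breach starts at three extra doses. The supply does not prevent it: 14 × 60 = 840 ml, or 840 / 120 = 7 bottles, limits the course total but not the amount in any one day.

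**Consequence for the primary outcome.** Section 9.7 does not say whether an overdose withdrawal stops follow-up as a consent withdrawal does under 7.10. If it does, each breach before day 10 removes one score under 10.8. The planned allowance for losses is 204 − 172 = 32 participants, so isolated cases would not threaten power. The documents give no rate from which to estimate how many there would be.

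**Lesser point: what a yes/no answer can support.** Doses due at four a day from day 1 are 12 (days 1–3), 16 (days 4–7) and 12 (days 8–10), total 40. If only yes/no is recorded, a yes at all three contacts means at least one missed dose in each interval. Doses taken could then be anything from 0 to 40 − 3 = 37. This is a logical bound and not a forecast, but it shows that no intermediate threshold could be applied.

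**Why the first-dose date matters.** Doses due by a contact on day 10 are 4 × (10 − first-dose day + 1): 40 for a day-1 start and 36 for a day-2 start. A report of 32 doses taken is then 32/40 = 80.0% or 32/36 = 88.9%. The day-2 start is an assumption; section 7 asks for an immediate start but allows courier delivery.

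**The case against.** The best counter-argument is that 8.6 means a late dose may be taken at any hour within the 60 ml total stated just before it. On that reading catch-up never exceeds the daily dose. This is possible, but the text does not say it. It also cannot cover the repeat-dose permission: a participant who takes all four doses and repeats one has swallowed 75 ml. One may reply that a repeated dose only replaces what was lost, but 9.7 does not say that a vomited dose is left out of the count.

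Second, 9.7 relies on conversations about the recommended dosage and on participants calling if they think they took too much, and not on the missed-dose question. That is fair. Such a conversation could reveal excess intake, and the telephone briefing before randomisation (7.1) could already mention a ceiling. The protocol requires neither a 24-hour amount nor a stated cap.

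Third, the breach needs three extra doses on top of a full day, and withdrawal applies only to a confirmed overdose. Both points stand, and they limit how often this can matter.

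On adherence, a reader might infer that the per-protocol analysis cannot be done. The documents do not support that. The case report form is not among them and may ask for a count. A set based on withdrawal, overdose or any reported missed dose would remain possible, and no share-of-doses set is promised; section 10.3 leaves the detail to a later SAP.

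A reader might also infer that participants followed by text or email escape the compliance check, because section 7 says "All follow up visits will occur either by phone, text or email depending on participant preference" while 8.11 says "Participants will be asked to confirm their compliance during planned telephone interviews with research staff on days 3,7,10 and 14". Section 8.11 can be read as a telephone check for everyone, so this is unstated detail and not a shown gap.

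**Conclusion.** The conflict between 8.6 and 9.7 stands on the text and does not depend on any document we lack. Three permitted extra doses on top of the scheduled four give 105 ml and meet the withdrawal rule; two give 90 ml and do not.

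Its practical size is unknown. The documents give no frequency of catch-up or vomiting and show no harm from 105 ml, so this should not be read as a demonstrated safety problem. The loss of a day-10 score depends on two conditions: the breach occurs before day 10, and the withdrawal ends data collection, which 9.7 leaves open. It would be wrong to conclude that the ITT analysis is biased or that the sample size is inadequate.

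The dose-count point is secondary. It concerns a sensitivity analysis only, and it applies only if the case report form records no number. It is worth acting on because the data cannot be recovered later and the change costs little.

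**What to change.** 1. In 8.6, and in the dosing instructions given to participants, state that catch-up and repeat doses must not take the total above 90 ml (six 15 ml doses) in any 24 hours.
2. At days 3, 7, 10 and 14, ask for the largest number of doses taken in any 24 hours since the last contact, in the same words whichever contact mode is used.
3. As the lesser change, replace the missed-dose item with the number of doses missed or taken since the last contact, and record the date of the first dose. Section 11.1 already requires dated case report forms, so contact dates should need no new item. If the per-protocol set is to use adherence, fix the threshold in the SAP before analysis.

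**Cost.** A minor amendment to the wording of 8.6, the follow-up items and the case report form. At an assumed one minute per contact, 204 × 4 × 1 = 816 minutes, about 13.6 staff hours over the trial. The answers remain self-reports from people who are ill, so a count will carry recall error. The ITT primary analysis method and the sample size stay as planned.

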7.1 Recruitment

Once patients notify the research team that they are happy to be contacted after a positive swab, the research team will then call the patients at home to see if they are still interested in taking part and send out the information sheet via email if they did not receive it at the swabbing station. If the patient does not have an email address they can arrange collection of the information sheet from site or it can be read out over the phone to them. Once they have had time to consider all the information and wish to take part, the research team will check all inclusion / exclusion criteria and eligibility. If they are not eligible the research team will explain why and ensure they have time to ask any relevant question they may have. If patients are eligible but decline they can do so without any reason.

For eligible patients wishing to take part, a link for an electronic consent form will be sent via email for e-signing. If this is not possible for any reason, then verbal consent will be taken over the telephone with the patients and two members of the research team. This will be recorded on a telephone consent form which will be read fully by the research team to the patients before consent is received. A copy of the telephone consent form will be sent to the patient's home with their randomised trial liquid. Enclosed will also be a blank copy of the full written consent form to send back via free post envelope supplied.

After consent research team will collect basic demographics, baseline VAS scores and check the patient's symptoms.

Eligible patients will be randomised 1:1, with no stratification, to either active treatment or placebo using REDCap software and be provided with the relevant bottles at full dosage, for 14 days. Dosage instructions will be provided on the labelling and will be discussed by the research team over the telephone prior to randomisation. Participants will have a contact number to contact the research team if they need to ask questions at any time.

7.1.1 Participant identification

Study posters will be left in A&E telling patients how they can take part if they receive a positive swab result. Patients will also be approached at the hospital swabbing tent if symptomatic on presentation for swabbing. Outpatient nurses carrying out the swabbing clinics will notify the research team of the time slots of any patient who might be eligible from their daily lists. No further details will be passed to researchers other than this.

A member of the research team will explain the study and ask if they would be happy to be contacted in the event that their swab comes back positive. If so, they will give the patient the Patient Information Sheet and will ask for their details to contact them after the swab result is returned.

Alternatively, patients can contact the research team later using the details on the poster, available at the swabbing station, in the event of a positive swab within the last 5 days.

At a non-EKHUFT swabbing site, patients will be approached by a member of the research team who will explain the study and ask if they would be happy to be contacted in the event that their swab comes back positive. If so, they will also give the patient the Patient Information sheet and ask for their details to contact them after the swab result is returned.

Alternatively, in the event of a positive swab, patients can contact the research team using the details on the poster displayed at the swabbing station.

Patients who have heard about the trial through the media or by seeing one of the approved posters may contact the Research Team directly. If they are able to show the positive swab test result that they have had a within the last 5 days, the research team will email them the Patient Information Sheet.

7.1.2 Screening

The only diagnostic test required will be the positive COVID result, which has already been taken. Proof of positive swab result will be requested at eligibility check. No other screening tests required.

7.1.3 Payment

There will be no payment for taking part in this trial.

7.2 Consent

For eligible patients wishing to take part, a link for an electronic consent form will be sent via email for e-signing. If this is not possible for any reason, then verbal consent will be taken over the telephone with the patients and two members of the research team. This will be recorded on a telephone consent form which will be read fully by the research team to the patients before consent is received. A copy of the telephone consent form will be sent to the patient's home with their randomised trial liquid.

Consent will be obtained by GCP trained research team members delegated the task by the PI. No trial procedures will occur before consent.

The Chief Investigator (CI) retains overall responsibility for the conduct of research at the site.

The taking of consent will be delegated to research staff and doctors who have been duly authorised, trained and competent to participate according to the ethically approved protocol, principles of Good Clinical Practice (GCP) and Declaration of Helsinki. A delegation log will be completed, checked and signed by the CI.

Only participants over the age of 18 years and capable of informed consent will be recruited.

Informed consent will be obtained prior to the participant being randomised and receiving Sambucol or placebo.

The right of a participant to refuse participation without giving reasons will be respected.

The participant will remain free to withdraw at any time from the trial without giving reasons and without prejudicing any further treatment and must be provided with a contact point where they may obtain further information about the trial. Data collected up to the point of withdrawal will only be used after withdrawal if the participant has consented for this on withdrawal. If a participant is required to re-consent or new information is required to be provided to a participant it is the responsibility of the PI to ensure this is done in a timely manner.

The CI takes responsibility for ensuring that all vulnerable participants are protected and participate voluntarily in an environment free from coercion or undue influence

7.2.1 Additional consent provisions for collection and use of participant data and biological specimens in ancillary studies, if applicable

No ancillary studies, no biological specimens collected.

7.3 The randomisation scheme

The method of randomisation

- Simple randomisation with a 1:1 allocation ratio with no stratification.
- Using REDCap software <https://www.project-redcap.org/>

7.3.1 Method of implementing the randomisation/allocation sequence

- Following consent, randomisation will be via REDCap using a randomisation list generated by the study statistician and uploaded onto REDCap.
- Team members are provided with login details and randomise patients by simply completing an on-screen form with patient details, inclusion and exclusion criteria. Treatment allocation is immediately available.

Investigators can view the details of patients they have previously randomised.

7.4 Blinding

The placebo has comparable appearance and taste to Sambucol® Black Elderberry Original Liquid.

Trial participants, trial statistician and outcome assessors will be blinded to which arm the participant has been randomised. Investigators, the research delivery team, clinical trial pharmacist and study staff not involved in assessing outcomes will not be blinded. All research delivery team members will be aware that they are not to divulge the randomised arm to participants at any time point.

Participants will remain blind to their allocated trial arm for the duration of the trial.

7.5 Emergency Unblinding

In case of serious adverse event, when deemed necessary by the investigator or treating health care professional, unblinding may be requested. A designated number will be provided on hospital systems and to patients in case unblinding needs to be performed by the research team. The CI will be contactable by the research team if necessary. It is thought unlikely unblinding will need to occur unless a new allergic reaction occurs to the food colouring in the liquid.

Documentation of the unblinding process including the reason and person who performed the unblinding, will be recorded in the site file. Thereby retaining the blinding of the outcome assessors.

An alert will be placed on the patient administration system (PAS) for the trust to advise clinicians that the participant is on the BERRY trial including contact details of who to contact for unblinding in an emergency. An assessment to unblind should be made in consultation with the clinical and research teams. If the decision is made to unblind the participants randomisation to the health professional, it will be expressed that the participant should not be given this information and that it should be shared only on a need to know basis. The medical team will be advised to document the act of unblinding in the patient notes, but not the randomised arm unless this is deemed essential for the participants ongoing care. This will maintain overall blinding in the trial. The treating health care professional will continue to deal with the participant's medical emergency as appropriate.

In all cases the Investigator will evaluate the causality and expectedness of SAEs as though the participant was receiving the active medication.

Unblinding and the reasons for doing so will be recorded on the CRF/data collection tool, in the site file and medical notes. It will also be documented at the end of the trial in any final trial report and/or statistical report

The CI/Investigating team will notify the Sponsor in writing as soon as possible following the unblinding and CI/PI will also notify the relevant authorities.

SUSARs are required to be reported unblinded.

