8 TRIAL TREATMENTS

8.1 Name and description of treatments

Sambucol® Black Elderberry Original (Sambucus nigra) Liquid

Constituents: 29.4 % (w/w) Black Elderberry (Sambucus nigra) fruit juice, 70% (w/w) of glucose syrup.

The main ingredient is black elderberry juice and it meets the requirements of the Directive

BERRY Protocol v 6.2 22.07.2021 IRAS 282732

2012/12/EU relating to fruit juices. The product also contains two food additives: citric acid (E330) as acidity regulator and potassium sorbate (E202) as preservative.

Primary packaging: Plastic PET amber bottles 120ml. Caps are PP28 white tamper-proof caps with security seal.

Secondary Packaging: None. Outer Carton: Cardboard 376mm x 191mm x 116mm. 32 bottles per case.

Placebo for Sambucol® Black Elderberry Original (Sambucus nigra) 120ml

Constituents: 70% (w/w) of glucose syrup, Flavouring agent: Elderberry Blossom. Colourants: Eurocert Carmoisine (311804) (E-122) and Eurocert Brilliant Black PN (419358) E-151. The product also contains two food additives: citric acid (E330) as acidity regulator and potassium sorbate (E202) as preservative.

Primary packaging: Plastic PET amber bottles 120ml. Caps are PP28 white tamper-proof caps with security seal.

Secondary Packaging: None. Outer Carton: Cardboard 376mm x 191mm x 116mm. 32 bottles per case.

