8.3 Product Characteristics

Sambucol® Black Elderberry Original (Sambucus nigra) Liquid has been used as a supplement since 1991 with no reports of adverse effects received by the Manufacturer.

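### Section 7.5 has SAE causality assessed as if on Sambucol, but the only reaction it foresees is to colourants listed only for the placebo, so such a reaction can escape SAR and SUSAR classification

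*Combined protocol and SAP*

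**What the plan says.** Section 7.5 (Emergency Unblinding) gives the rule: "In all cases the Investigator will evaluate the causality and expectedness of SAEs as though the participant was receiving the active medication". Earlier in the same section, on when unblinding might be needed, it says: "It is thought unlikely unblinding will need to occur unless a new allergic reaction occurs to the food colouring in the liquid". It does not say which liquid is meant.

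Section 8.1 gives the contents of each liquid.

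- Sambucol: "Constituents: 29.4 % (w/w) Black Elderberry (Sambucus nigra) fruit juice, 70% (w/w) of glucose syrup". It adds: "The product also contains two food additives: citric acid (E330) as acidity regulator and potassium sorbate (E202) as preservative". No colourant is listed.
- Placebo: glucose syrup, an elderberry blossom flavouring, the same two additives, and "Colourants: Eurocert Carmoisine (311804) (E-122) and Eurocert Brilliant Black PN (419358) E-151".

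Section 6.2 excludes people with a known allergy to food colourants, so only a new allergy could arise in the trial.

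On who knows the allocation, section 7.4 says: "Investigators, the research delivery team, clinical trial pharmacist and study staff not involved in assessing outcomes will not be blinded". On the safety record, section 8.3 says that Sambucol "has been used as a supplement since 1991 with no reports of adverse effects received by the Manufacturer". No equivalent statement is given for the placebo.

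Section 9.1 defines a SAR by attribution to either of the trial treatments, not to Sambucol alone. Under 9.2, definite, probable and possible causality make an event an adverse reaction; unlikely and unrelated leave it as an adverse event. Under 9.3, SAEs go to the sponsor within 24 hours, and those rated both related and unexpected become SUSARs, which go to the REC and the manufacturer. Section 7.5 requires SUSARs to be reported unblinded.

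**The concern.** Assuming active treatment is a sensible precaution when the assessor is blinded and the placebo is inert, because any error then leans towards reporting. Here the comparator contains ingredients that the active product is not listed as containing, and the protocol itself names a reaction to that kind of ingredient as the likeliest reason to unblind. For that reaction the rule directs the assessor to the liquid without the suspected ingredient.

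Causality decides whether an SAE becomes a SAR, and causality with expectedness decides whether it becomes a SUSAR. An instruction that allows a true placebo reaction to be rated unrelated can therefore keep a harm caused by the trial's own comparator out of expedited reporting.

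**Working it through.** **1. Who is exposed.** Section 10.1 plans 204 participants. With SD 20, difference 10, 90% power and 5% significance (two-sided assumed), the normal approximation gives 2 × (1.960 + 1.282)² × (20/10)² = 84.06, so 85 per group. The t-test version gives 85.03, so 86, as stated. Then 86/0.85 = 101.2, rounded up to 102 per group, or 204. The figure reproduces and this point does not affect it. With simple 1:1 allocation, about 102 participants receive the listed colourants and about 102 receive none.

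**2. Following one event through the rules.** Take a placebo participant with a serious allergic reaction that is recorded as an SAE.

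| Situation | Assessed as if on Sambucol (7.5) | Result under 9.1 to 9.3 |
|---|---|---|
| Cause not pinned down | Allergy to an ingredient is plausible (2.1 allows for it) and the timing fits: at least possible | Adverse reaction; SAR; SUSAR if unexpected, reported unblinded |
| Colourant identified as the cause | Sambucol lists no colourant, and another documented cause is most plausible: unlikely or unrelated | Adverse event only; SAE to sponsor; no SAR or SUSAR |
| Same event under the 9.1 SAR definition | Not applied as if on Sambucol; due to one of the two liquids: related | SAR; SUSAR if unexpected |

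Rows two and three give opposite answers for the same event. The contradiction lies between 7.5, 8.1 and 9.1 and needs no outside figure.

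**3. Expectedness.** Sections 8.3 and 8.8 report no known adverse effects of Sambucol. Once an event is rated related, measuring it against Sambucol tends to make it unexpected, and so reportable. The difficulty is therefore with causality.

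**4. Does the rule protect a blind?** Section 7.4 leaves investigators unblinded, 7.3.1 makes the allocation available at once, and 8.4 marks batches Q or Z. On that reading the rule conceals nothing. The closing words of the 7.4 sentence could be read as limiting the whole list to staff who do not assess outcomes, and section 1 mentions blinded investigators. Even for a blinded assessor, checking against both ingredient lists would reveal no allocation.

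**5. How often.** The documents give no colourant reaction rate. For scale only, the chance of at least one serious colourant reaction among 102 placebo participants is 1 − (1 − p)^102:

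| Assumed p | Chance of at least one |
|---|---|
| 0.05% | 5% |
| 0.1% | 10% |
| 0.5% | 40% |
| 1% | 64% |

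At a given rate these are upper limits for the problem, because the event must also follow row two.

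**The case against.** The strongest reply is that other sections contain most of the damage.

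- **Charging the event to Sambucol.** A reader might infer that placebo reactions will be attributed to Sambucol. The documents do not support that. A related and unexpected event is a SUSAR and is reported unblinded, safety is analysed by randomised arm (10.7), and the batch number in the CRF identifies the liquid. The event would be counted under placebo. This part of the reply stands.
- **Dismissal as the rule.** Nor does the protocol make dismissal automatic. Under 9.2 plausibility and timing suffice for a rating of possible, 9.1 counts an event as a reaction when a link cannot be ruled out, and a rating of unlikely or unrelated needs another documented cause. This also stands, and it narrows the problem to cases where the colourant has been identified.
- **Recording.** SAEs reach the sponsor whatever their causality. That holds for those recorded as SAEs. Section 9.2 leaves out listed COVID-19 manifestations, including shortness of breath and rash, while 2.1 names difficulty breathing as a sign of severe allergy. For deaths, 9.5 makes notification depend on causality, in tension with 9.3.
- **Scope.** Under its heading, the opening phrase of the rule may mean all unblinding cases, not every SAE. Either reading includes the colouring reaction, since that is the unblinding case 7.5 foresees. The rule does not reach non-serious allergy.

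What remains is row two of the first table. Unblinded SUSAR reporting cannot rescue that event, because it applies only after the event has been rated related.

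**Conclusion.** The concern holds as a limited internal contradiction. Section 7.5 can lead to a serious placebo reaction, correctly traced to the colourant, being rated unlikely or unrelated. It would then bypass SAR and SUSAR handling, while section 9.1 would class the same event as a SAR. A recorded SAE would still go to the sponsor.

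The size is small in events and cannot be estimated from the documents. It is tempting to say that assessment goes wrong in every colourant case, because all listed exposure is in one arm. That is a statement about exposure (about 102 against none), not an error rate. Nor does the rule make Sambucol look safer by arm: any imbalance would come from the placebo's ingredients and would appear in by-arm counts whatever the rule says.

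The conclusion assumes that the ingredient lists in 8.1 are complete. The reference safety information is a separate document not included here, so what it says about the placebo is unknown.

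**What to change.** Reconcile 7.5 with 9.1 by replacing the sentence in 7.5 with:

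> Causality will be assessed against the listed ingredients of both trial liquids (section 8.1); an event that could reasonably be due to an ingredient of either liquid is classed as related.

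Expectedness then rests on the reference safety information, as 9.1 and 9.4 already provide. In the final report, attribute related events to the liquid actually taken, using the recorded batch number.

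Do not add colourant hypersensitivity to the reference safety information as an expected event. A SUSAR must be both related and unexpected, so listing it could remove the expedited reporting that this change is meant to secure.

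The cost is one sentence in 7.5 and one reporting line. A few more SAEs may be classed as possibly related, which is the cautious direction. Sample size, randomisation and the efficacy analysis are unchanged.
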